### Amendment rationale

This amendment is implemented to:

- Increase the size of the target population.
- Clarify the planned number of bone biopsies and bone densitometry and MRI assessments.

### Detailed description of changes

Minor editorial changes, such as the correction of typing errors, are not specifically listed.

In the table below, deleted text is crossed out and new text is highlighted using italics.

Changes to this protocol include:	
Formerly read:	Now reads:
Section 1.5.1: Sample size rationale	
The sample size is intended to maximize available safety data to support product registration. <del>In combination with subjects receiving active treatment in the ongoing placebo-controlled trial (KF7013-01) and further planned trials of neridronic acid, the number of subjects included in this trial is intended to support regulatory requirements for at least 500 subjects evaluated for safety.</del> It is estimated that approximately 220 subjects will be included in this trial; <del>the actual number of subjects allocated, however, may depend on enrollment in ongoing and further planned trials.</del>	The sample size is intended to maximize available safety data in line with the FDA regulatory requirements to support product registration. It is estimated that approximately 290 subjects will be included in this trial.
Section 1.6: Schedule of events	
u) <del>Bone densitometry (DXA) and MRI will be performed</del> in a subset of 30 subjects . v) A single bone biopsy will be obtained from the iliac crest, following tetracycline double-labeling, in a subset of subjects. The biopsy should be scheduled to be performed 26 weeks after the first administration of IMP. <del>Biopsies will be obtained from approximately 20 subjects to obtain 15 evaluable biopsy specimens.</del>	u) It is planned to perform bone densitometry (DXA) and MRI in a subset of 30 subjects. v) A single bone biopsy will be obtained from the iliac crest, following tetracycline double-labeling, in a subset of subjects. The biopsy should be scheduled to be performed 26 weeks after the first administration of IMP. It is planned to obtain approximately 15 evaluable bone biopsy samples from approximately 20 subjects.
Section 8.1: Discussion of the trial design	
Normal bone mineralization and bone formation were observed in biopsies from regions of non-pagetic bone (iliac crest), and improved indices of bone turnover were observed in regions of pagetic bone. <del>Biopsies will be obtained from approximately 20 subjects to obtain 15 evaluable biopsy specimens.</del> It is anticipated that <del>15 evaluable biopsy specimens will be adequate to</del> confirm normal bone mineralization in the iliac crest at approximately 6 months following treatment with neridronic acid 400 mg. A 6 month time point was selected for the biopsy in order to match the slow kinetics of bone matrix and mineral apposition in	Normal bone mineralization and bone formation were observed in biopsies from regions of non-pagetic bone (iliac crest), and improved indices of bone turnover were observed in regions of pagetic bone. It is planned to obtain approximately 15 evaluable bone biopsy specimens from approximately 20 subjects. It is anticipated that bone biopsy specimen evaluation will confirm normal bone mineralization in the iliac crest at approximately 6 months following treatment with neridronic acid 400 mg. A 6 month time point was selected for the biopsy in order to match the slow kinetics of bone matrix and mineral apposition in

Changes to this protocol include:	
Formerly read:	Now reads:
humans, with approximately 6 months required to complete a single remodeling cycle (Riggs and Parfitt 2005). A subset of 30 subjects will undergo bone densitometry and MRI to assess the effect of neridronic acid on BMD...	humans, with approximately 6 months required to complete a single remodeling cycle (Riggs and Parfitt 2005). It is anticipated that a subset of 30 subjects will undergo bone densitometry and MRI to assess the effect of neridronic acid on BMD...
Section 11.1.1.1: Visit 1 (Day -60 to Day -1)	
• Perform bone imaging (DXA and MRI will be performed in a subset of 30 subjects [from US sites only]).	• Perform bone imaging (DXA and MRI will be performed in a subset of approximately 30 subjects [from US sites only]).
Section 11.1.3.4: Visit 9 (Week 26; ±15 days)	
A single bone biopsy will be obtained from the iliac crest, following tetracycline double-labeling, in a subset of subjects (from US sites only). The biopsy should be scheduled to be performed 26 weeks after the first administration of IMP. Biopsies will be obtained from approximately 20 subjects to obtain 15 evaluable biopsy specimens. [...] • Perform bone imaging (DXA and MRI will be performed in a subset of 30 subjects [from US sites only]).	A single bone biopsy will be obtained from the iliac crest, following tetracycline double-labeling, in a subset of subjects (from US sites only). The biopsy should be scheduled to be performed 26 weeks after the first administration of IMP. Biopsies will be obtained from approximately 20 subjects to obtain approximately 15 evaluable biopsy specimens. [...] • Perform bone imaging (DXA and MRI will be performed in a subset of approximately 30 subjects [from US sites only]).
Section 14.1.1: Sample size rationale	
Subset of subjects for bone biopsies The sample size is not based on statistical considerations; <del>15 evaluable biopsy specimens are considered adequate to be able to</del> identify qualitative bone abnormalities such as osteomalacia as well as quantitative indicators of impaired mineralization. Subset of subjects for bone densitometry and magnetic resonance imaging The sample size is not selected based on statistical considerations. Results from <del>30</del> subjects are considered to be sufficient to demonstrate feasibility and <del>support a rationale for the future use</del> of these assessments in trials of neridronic acid in CRPS.	Subset of subjects for bone biopsies The sample size is not based on statistical considerations; bone biopsy specimen evaluation will identify qualitative bone abnormalities such as osteomalacia as well as quantitative indicators of impaired mineralization. Subset of subjects for bone densitometry and magnetic resonance imaging The sample size is not selected based on statistical considerations. Results from this subset of subjects are considered to be sufficient to demonstrate feasibility and explore outcomes of these assessments in trials of neridronic acid in CRPS.

## 2 ABBREVIATIONS

Abbreviation	Explanation
ACR	Albumin creatinine ratio
ADaM	Analysis Data Model
ALT	Alanine aminotransferase
AST	Aspartate aminotransferase
BAP	Bone alkaline phosphatase
β-HCG	β-human chorionic gonadotropin
BMI	Body mass index
BPI	Brief Pain Inventory
CES-D	Center for Epidemiological Studies Depression Scale
CI	Confidence interval
CIR	Crude incidence rate
CRPS	Complex regional pain syndrome
CTX	C-terminal telopeptide of type I collagen
DMC	Data monitoring committee
ECG	Electrocardiogram
eCRF	Electronic case report form
eGFR	Estimated glomerular filtration rate
EQ VAS	EuroQol visual analog scale
EQ-5D-5L	EuroQol 5-dimension 5-level questionnaire
EU	European Union
FAS	Full Analysis Set
ICTR	Integrated clinical trial report
ID	Identification
IMP	Investigational medicinal product
IRT	Interactive response technology
LSmeans	Least square means
MDMA	3,4-methylenedioxy methamphetamine, ecstasy
MedDRA	Medical Dictionary for Regulatory Activities
Min	Minimum
MMRM	Mixed effects model for repeated measures
MNAR	Missing-not-at-random
MRI	Magnetic resonance imaging
N, n	Number of subjects
nMiss	Number of missing values
NRS	Numerical rating scale
PASS	Pain Anxiety Symptom Scale
PDI	Pain Disability Index

Abbreviation	Explanation
PD Set	Pharmacodynamic Set
PGIC	Patient Global Impression of Change
PPS	Per Protocol Set
PINP	Procollagen type I amino-terminal propeptide
PT	Preferred Term
Q1	First quartile
Q3	Third quartile
QTcB	Corrected QT interval (according to Bazett's formula)
QTcF	Corrected QT interval (according to Fridericia's formula)
SAF	Safety Set
SAP	Statistical analysis plan
SAS	Statistical analysis software®
SD	Standard deviation
SI	Système International d'Unités
SOC	System Organ Class
SDTM	Study Data Tabulation Model
TCS	Treatment Completers Set
TEAE	Treatment emergent adverse event
ULN	Upper limit of normal
USA	United States of America
VAS	Visual analog scale
WHO-DD	World Health Organization Drug Dictionary

Système International d'Unités units are not included in this list.

### **3 INTRODUCTION**

This statistical analysis plan (SAP) includes all definitions and analysis details for the analysis of the trial KF7013-03 in accordance with the protocol version 5.0 dated 17 Nov 2017, and the eCRF DMS version 5.0 dated 28 Jul 2017. The analysis will be performed by a contract research organization in accordance with this SAP.

### **4 TRIAL OBJECTIVES**

Primary objective:

- To assess the safety and tolerability of neridronic acid in subjects with CRPS.

Secondary objectives:

- To assess the safety and tolerability of neridronic acid in subjects with CRPS.
- To assess the efficacy of neridronic acid in the treatment of CRPS.

## 5 TRIAL DESIGN

### 5.1 Overall trial design and plan

Only a brief synopsis of the trial design is presented here; full details can be found in the trial protocol.

This is a multi-site, open-label, single-arm, Phase III safety trial of intravenous neridronic acid in subjects with CRPS.

There will be an enrollment period lasting up to 60 days, a treatment period consisting of 4 infusions over 10 days, and a follow-up period of approximately 50 weeks (Visit 6 [Week 2] through Visit 11 [Week 52]). The subjects are expected to be in the trial for approximately 60 weeks (14 months). See [Figure 1](#) for a summary of the trial as a flow diagram. For details, refer to the schedule of events defined in the trial protocol.

[figure not shown]

Figure 1: Flow diagram summary of the trial

The investigational medicinal product (IMP) is 100 mg neridronic acid diluted in 500 mL normal saline and administered by slow intravenous infusion (240 minutes [maximum 260 minutes]) at Visit 2, Visit 3, Visit 4, and Visit 5, resulting in a total dose of 400 mg neridronic acid.

In addition to the assessments applicable to all trial subjects, bone biopsies will be performed in a subset of trial subjects to assess the bone safety of neridronic acid 400 mg. In addition, bone imaging assessments (bone densitometry and magnetic resonance imaging) will be performed in a subset of trial subjects. Bone biopsies and bone imaging data will only be obtained from subjects participating at sites in the United States of America (USA).

An external independent data monitoring committee (DMC) will periodically review safety information from the trial and monitor trial conduct and overall progress.

### 5.2 Sample size

The sample size is intended to maximize available safety data to support product registration. In combination with subjects receiving active treatment in the ongoing placebo-controlled trial (KF7013-01) and further planned trials of neridronic acid, the number of subjects included in this trial is intended to support regulatory requirements for at least 500 subjects on neridronic acid evaluated for safety. It is estimated that approximately 290 subjects will be included in this trial.

For bone biopsies, results from 15 evaluable biopsy specimens are considered adequate to be able to identify qualitative bone abnormalities such as osteomalacia as well as quantitative indicators of impaired mineralization.

For bone densitometry and magnetic resonance imaging (MRI) assessments, results from 30 subjects are considered sufficient to demonstrate feasibility and support a rationale for the future use of these assessments in trials of neridronic acid in CRPS.

If the expected number of bone biopsies or bone densitometry and MRI assessments are not obtained, it is not planned to increase the number of subjects included in the trial.

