### 1.5.1 Sample size rationale

The sample size is intended to maximize available safety data in line with the FDA regulatory requirements to support product registration. It is estimated that approximately 290 subjects will be included in this trial.

If the expected number of bone biopsies or bone densitometry and MRI assessments are not obtained, it is not planned to increase the number of subjects included in the trial.

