##### **Subset of subjects for bone biopsies**

The sample size is not based on statistical considerations; bone biopsy specimen evaluation will identify qualitative bone abnormalities such as osteomalacia as well as quantitative indicators of impaired mineralization.

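### SAP 5.2 calls 15 bone biopsies adequate to identify osteomalacia; the protocol gives that number no statistical basis, and 0 of 15 would still be compatible with a rate of about 22%

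*SAP*

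**What the plan says.** SAP Section 3 says the SAP accords with protocol version 5.0 of 17 November 2017. Under the heading Sample size, SAP 5.2 says that "results from 15 evaluable biopsy specimens are considered adequate to be able to identify qualitative bone abnormalities such as osteomalacia"; the same sentence extends the claim to quantitative indicators of impaired mineralization.

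Protocol 14.1.1, on the biopsy subset, reads differently: "The sample size is not based on statistical considerations; bone biopsy specimen evaluation will identify qualitative bone abnormalities such as osteomalacia". It attaches no number to that statement. Protocol 8.1 plans about 15 evaluable specimens from about 20 subjects and anticipates that their evaluation will confirm normal mineralization in the iliac crest at about 6 months.

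Protocol 14.1.6.3 makes osteomalacia a yes/no outcome per subject: osteoid thickness above 12.5 µm together with mineralization lag time above 100 days. It plans descriptive summaries. SAP 15.4 lists the eCRF biopsy data, plans no further analysis and leaves the rest to a separate provider. SAP 7.1, which lists changes from the protocol, does not mention the adequacy claim.

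Two other sentences in SAP 5.2 also differ from the protocol. The overall number "is intended to support regulatory requirements for at least 500 subjects on neridronic acid evaluated for safety", pooled with other trials, whereas Protocol 1.5.1 says "The sample size is intended to maximize available safety data in line with the FDA regulatory requirements to support product registration". The imaging subset is said to support a case for later use of the assessments, where Protocol 14.1.1 speaks only of exploring their outcomes.

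**The concern.** The SAP makes a numerical adequacy claim that its governing protocol does not make, and it supports the claim with no rate, detection probability or precision. The biopsies are a bone-safety assessment in a trial meant to support registration, and the protocol already states the result it expects. If no case is seen, a reader would have a pre-stated claim that 15 is adequate next to a pre-stated expectation of normal mineralization, and no planned interval showing how little 15 specimens can exclude.

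**Working it through.** **Is there a figure to reproduce?** No. SAP 5.2 gives the number 15 and nothing else, and Protocol 14.1.1 disclaims a statistical basis. The check is therefore what 15 specimens can show.

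**Inputs**
- n = 15 evaluable specimens (SAP 5.2; about 15 in Protocol 8.1).
- Event: the per-subject osteomalacia definition in Protocol 14.1.6.3.
- Confidence level: 95% (Protocol 14.1.2).
- True rate p: not in the documents. Rates from 1% to 20% are assumed for illustration.

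**Probability of seeing no case**, P(0 of n) = (1 − p)^n, with n = 15:

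| Assumed true rate | P(no case) | P(at least one case) |
|---|---|---|
| 1% | 0.99^15 = 0.860 | 0.140 |
| 2% | 0.98^15 = 0.739 | 0.261 |
| 5% | 0.95^15 = 0.463 | 0.537 |
| 10% | 0.90^15 = 0.206 | 0.794 |
| 20% | 0.80^15 = 0.035 | 0.965 |

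**Rate that 15 specimens would reveal with a given probability**, p = 1 − (1 − target)^(1/15):
- 80%: 1 − 0.20^(1/15) = 10.2%
- 90%: 1 − 0.10^(1/15) = 14.2%
- 95%: 1 − 0.05^(1/15) = 18.1%

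**Upper 95% limit when no case is seen.** This needs no assumed rate.
- Two-sided exact (Clopper-Pearson): 1 − 0.025^(1/15) = 21.8%
- One-sided: 1 − 0.05^(1/15) = 18.1%

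**Sensitivity to the number actually evaluable**, no case seen:

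| n | Two-sided upper limit | One-sided upper limit | P(no case) at an assumed 5% |
|---|---|---|---|
| 12 | 26.5% | 22.1% | 0.540 |
| 14 | 23.2% | 19.3% | 0.488 |
| 15 | 21.8% | 18.1% | 0.463 |
| 16 | 20.6% | 17.1% | 0.440 |
| 20 | 16.8% | 13.9% | 0.358 |

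Even if all 20 planned subjects gave an evaluable specimen, zero cases would leave a rate of nearly 17% within the two-sided interval. Both documents say that the trial will not be enlarged if biopsies fall short.

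**The case against.** The strongest reply is that SAP 5.2 contains no arithmetic error. It states no rate or power, the trial is exploratory with no inferential testing, and the sentence can be read as saying that biopsy is a method capable of showing osteomalacia. Protocol 14.1.1 uses capability language of that kind under its own sample-size heading, so the heading alone does not settle the meaning. The sentence also covers quantitative indices, which are continuous, and a zero-event calculation says nothing about those.

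Much of this stands. No figure in the SAP is miscalculated, and the calculation bears only on the yes/no osteomalacia outcome. The capability reading does not fully rescue the sentence, however: its subject is results from 15 specimens, and a method's capability does not depend on 15.

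Three stronger readings are tempting, and the documents do not support them.
- A reader might infer that the SAP plans to report zero cases as proof of normal bone. It does not. SAP 15.4 plans listings only, and the expectation of normal mineralization is in Protocol 8.1.
- A reader might infer that the protocol has dropped all detection language. It has dropped only the adequacy of a number; Protocol 14.1.1 still says, without qualification, that evaluation will identify abnormalities.
- A reader might infer from the 500-subject sentence that the trial is wrongly sized. SAP 5.2 and Protocol 1.5.1 both give about 290, and a pooled target does not contradict a general reference to FDA requirements.

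**Conclusion.** The adequacy claim in SAP 5.2 is unsupported and is an undeclared departure from protocol version 5.0. Zero cases in 15 would leave an osteomalacia rate of up to 21.8% within the two-sided exact 95% interval (18.1% one-sided), so it could not by itself confirm normal mineralization. Under assumed true rates of 2%, 5% and 10%, zero cases would be seen with probability 74%, 46% and 21%. These three rates are illustrations; the upper limit does not depend on them. All the figures assume independent subjects and perfect histological detection, and the headline figures assume exactly 15 evaluable specimens.

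The consequence is limited to how the biopsy result is described and interpreted. It changes neither the planned number of subjects nor the primary endpoint, and it gives no ground for saying that more biopsies are required. The 500-subject and imaging sentences are editorial mismatches that change no result.

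**What to change.** 1. **SAP 5.2.** Delete the adequacy sentence. Say that the biopsy number was not chosen on statistical grounds, and state the precision; for example, 0 of 15 gives a two-sided exact 95% upper limit of about 22%. Copying the Protocol 14.1.1 sentence is not enough, because it would bring in the unqualified statement that evaluation will identify abnormalities.
2. **SAP 15.4, or the biopsy provider's analysis specification.** Report the number of subjects meeting the Protocol 14.1.6.3 definition, with a two-sided exact 95% interval. Two-sided fits the protocol's general 95% confidence intervals. The denominator should be the subjects actually evaluable for both components of the definition; the Bone Biopsy Set also admits subjects evaluable for histology alone. Because SAP 15.4 assigns the analysis elsewhere, the SAP should say which document carries this output.
3. **Interpretation.** Limit any conclusion about osteomalacia, including the expectation in Protocol 8.1, to what that interval excludes.
4. **Same edit.** Align the 500-subject sentence with Protocol 1.5.1 and the imaging sentence with Protocol 14.1.1.

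The cost is a SAP wording change, one added interval, possibly a line in the provider's specification, and a precision statement less favourable than the present claim. No extra biopsies or subjects are needed.

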### 5.3 Randomization

Not applicable.

## 6 OVERVIEW OF PLANNED ANALYSES

### 6.1 Final analysis

The final analysis will be performed after all subjects have completed the trial, and the data has been hard locked. The results of the final analysis will be the basis for the integrated clinical trial report.

### 6.2 Interim analyses

An external DMC will periodically review safety information from the trial and monitor trial conduct and overall progress. For details on the interim analysis, please refer to Section 17.

## 7 DOCUMENT AND CHANGE HISTORY

### 7.1 Changes in analysis compared to the trial protocol

This section summarizes the changes in the analysis compared to the protocol.

Protocol	SAP
Section 1.5.2 Full Analysis Set: All subjects who are allocated and treated.	Section 9.4 The Full Analysis Set includes all subjects allocated with at least 1 IMP administration, including any partial infusion . Reason: To align with the definition of the SAF.
Section 14.1.3 The Pharmacodynamic Set includes all subjects with at least 1 non-missing value for at least 1 of the bone turnover markers.	Section 9.4 The Pharmacodynamic Set includes all treated subjects with at least 1 non-missing value for at least 1 of the bone turnover markers Reason: Only treated subjects were intended for inclusion in this analysis set.

### 7.2 Rationale for changes from pre-final to final SAP

Not applicable.

### 7.3 SAP amendment rationale

The rationale for amendment 01 on the final SAP is to implement the changes resulting from the protocol amendments and project decisions . In addition, minor corrections and revisions were performed.

In the table below, deleted text is crossed out and new text is highlighted using italics.

Change from final	Rationale for change

Section 3
 
This statistical analysis plan (SAP) includes all definitions and analysis details for the analysis for DMC periodic meetings of the trial KF7013-03 in accordance with the protocol version 4.05.0 dated <del>19 Apr 17 Nov 2017</del>, and the eCRF version <del>4.0 5.0 dated 17 Nov 2016</del> 28 Jul 2017. The analysis will be performed by a contract research organization in accordance with this SAP.
	
Update to the latest version of protocol and eCRF.

Section 5.1
 
The sample size is intended to maximize available safety data to support product registration. In combination with subjects receiving active treatment in the ongoing placebo-controlled trial (KF7013-01) and further planned trials of neridronic acid, the number of subjects included in this trial is intended to support regulatory requirements for at least 500 subjects evaluated for safety. It is estimated that approximately <del>220-290</del> subjects will be included in this trial; <del>the actual number of subjects allocated, however, may depend on enrollment in ongoing and further planned trials.</del>
	
According to Protocol Amendment 5, the sample size was increased.

Section 8.2.1
 
<del>Not applicable.</del>
 
Two subgroups will be defined based on the duration of CRPS:
 
1. Subjects with duration <math>\leq 2</math> year from onset of symptoms suggestive of CRPS.
 
2. Subjects with duration <math>> 2</math> year from onset of symptoms suggestive of CRPS.
 
When subgroup analyses are specified, the analysis will be performed separately in each of the subgroups and overall.
	
To add subgroup analyses.


Section 10.2
 
Reasons for discontinuations from the trial and from IMP will be presented for:
 
 
• Subjects allocated and discontinued from the trial
 
• Subjects allocated and discontinued IMP intake.
 
• Subjects allocated and discontinued from the trial per trial phase, i.e., during the treatment period, and during the follow-up period <del>overall, and separately for the first 100 subjects (Visit 11) and for subsequent subjects (Visit 9).</del>
 
	
According to Protocol Amendment 1 from 21 Oct 2016, the design of the trial was changed, all subjects are treated and analyzed in the same way, no need for separate analyses.

Section 13.2
 
The following secondary efficacy endpoints will be analyzed overall and by subgroups:
 
Change from baseline to Week 12 and Week 26 in the current pain intensity score, using a numerical rating scale (NRS).
 
 
• Response to treatment, defined as at least 30%, <del>and</del> at least 50% and at least 2 points on the NRS decrease from baseline in the current pain intensity score, at Week 12 and Week 26.
 
• Patient Global Impression of Change (PGIC) at Week 12 and Week 26.
 
• Change from baseline to Week 12 and Week 26 in the Pain Interference score of the Brief Pain Inventory (BPI).
 
	
To add subgroup analysis for secondary efficacy endpoints and add ‘at least 2 points on the NRS’ in the responder analyses

Section 13.2.1.2
 
Descriptive summaries of the responder status will be presented by visit for each of the 3 responder definition. This includes the summary of the secondary responder endpoints, i.e., the response to treatment defined as at least 30%, <del>and</del> at least 50% and at least 2 points on the NRS decrease from baseline at Week 12 (Visit 8) and Week 26 (Visit 9).
	
To add ‘at least 2 points on the NRS’ in the responder analyses

Section 13.3
 
The following outcome parameters based on other efficacy data collected in this trial will be analyzed for the FAS:
	
To add analysis population for other efficacy data.

Section 15.2.1
 
In table 3, mean plot and shift plot are added for parathyroid hormone, vitamin D and calcium.
	
To align with the analyses for DMC


Section 20.1.1.14
 
If the last available visit is between Visit 2 and Visit 7, data from the early termination visit will be assigned to the next scheduled visit; otherwise <del>Visit 9 or Visit 11 in the follow-up period.</del> Data will be assigned to the nearest scheduled visit based on the trial day of the early termination visit and the planned visit day. The planned visit day is:
 
 
• Day 182 for Visit 9 (Week 26).
 
• Day 273 for Visit 10 (Week 39).
 
• Day 365 for Visit 11 (Week 52).
 
	
To specify the imputation methods and programming instructions more clearly.

Section 19.2
 
<del>Not applicable.</del>
 
Changes are made from Final SAP version 1.0 to SAP Amendment Version 2.0, all the changes are documented in Section 7.3.
	
To document the changes in the versions of SAP.

